3.2 Rationale for Study Design

3.2.1 Dose Selection

The rationale for dose selection is described in Section 1.5.

3.2.2 Outcome Variable Selection

3.2.2.1 Safety

The study is designed to primarily evaluate the safety and tolerability of long-term treatment with sebelipase alfa, administered by weekly and biweekly IV infusions. As such, the main outcome variables in this study will assess safety and tolerability of sebelipase alfa in adult patients with liver dysfunction due to LAL Deficiency, and will include:

- Changes from baseline in vital signs, physical examination findings, clinical laboratory tests, and 12-lead electrocardiogram (ECG) parameters.
- The incidence of AEs, SAEs, and IARs.
- Use of concomitant medications/therapies.
- Characterization of ADAs, including ADA positivity rate, time to ADA positivity, median and peak ADA titer, and time to peak ADA titer.

Page 23 of 76

- Given the potential for ADAs to alter the safety profile of sebelipase alfa, a subgroup analysis will be conducted comparing safety endpoints in ADA-positive and ADA-negative subjects.
- A further characterization of ADAs, including inhibitory ADAs, may be performed as a separate pooled analysis across studies, and will be reported separately from this protocol.

3.2.2.2 Efficacy

The biological effects of ERT for LAL Deficiency have not been fully established. However, any successful therapy for late onset LAL Deficiency must be able to mitigate the progressive liver deterioration that is a predominant clinical feature of this disorder. The following efficacy measures will be utilized to investigate the effect of sebelipase alfa on hepatic dysfunction in LAL Deficiency:

- Liver and spleen volume by magnetic resonance imaging (MRI).
- Liver and spleen fat content by multi-echo gradient-echo MRI and ¹H magnetic resonance spectroscopy (MRS) (if available).
- Liver cholesteryl ester signature (as measured by ¹³C MRS) in a subset of subjects receiving treatment at sites with access to this imaging technology.
- An assessment of hepatic histopathology will also be conducted in those subjects who agree to an optional liver biopsy.

3.2.2.3 Pharmacodynamics

Based on a review of the literature, input from experts in the field, and insights from the nonclinical disease model (Section 1.3), the following biomarkers will also be investigated for their potential utility in describing pharmacodynamic responses to sebelipase alfa:

- Serum transaminases
- Serum lipids
- Acute phase reactants (e.g., serum ferritin)

Blood and urine samples will also be collected to support exploratory analyses of changes or percent changes from baseline in additional disease-related biomarkers, which may be identified based on emerging information from the sebelipase alfa development program and scientific literature.

Given the potential for ADAs to alter the PD effect of sebelipase alfa, a subgroup analysis will be conducted for the efficacy and PD endpoints comparing ADA-positive and ADA-negative subjects.

3.2.2.4 Health-Related Quality of Life (HRQOL) Outcomes

Based on the effects of ERT in other diseases, significant health benefits are anticipated with sebelipase alfa treatment. As there are currently no validated tool(s) to assess HRQOL in LAL Deficiency, HRQOL will be assessed using tools developed for other diseases. Changes in

Page 24 of 76

scores for the 36-item Short Form (SF 36[®]) Health Survey, Functional Assessment of Chronic Illness Therapy-Fatigue (FACIT-Fatigue) scale, and Chronic Liver Disease Questionnaire (CLDQ) will be determined. Positive treatment effects on HRQOL will provide supporting evidence of sebelipase alfa treatment benefit.

3.2.2.5 Pharmacokinetics

The preliminary clinical pharmacokinetics of seblipase alfa will be characterized in study LAL-CL01. Clinical pharmacokinetic data will continue to be collected in this extension study to permit a more robust assessment of sebelipase alfa pharmacokinetics. This will include the steady state pharmacokinetic profile of the qow dosing regimen and an assessment of the impact of ADAs (if any) on sebelipase alfa pharmacokinetics. PK parameters will include maximum observed serum concentration (C_{max}), minimum observed serum concentration (C_{min}), area under the serum concentration-time curve from time zero extrapolated to infinity (AUC_{inf}), terminal elimination half-life ($T_{1/2}$), apparent serum clearance (CL), and steady state volume of distribution (V_{ss}).

3.2.3 Study Duration

Given the progressive and potentially life-threatening nature of untreated LAL Deficiency, and the low likelihood that beneficial effects of sebelipase alfa therapy will be maintained after discontinuation of treatment, subjects enrolled in this extension study will be given the option to continue to receive treatment under this protocol. Each patient may receive up to 5 years of treatment under this protocol.

4 Study Population

4.1 Target Population

The target population for this study is male and female subjects (\geq 18 years of age) with liver dysfunction due to LAL Deficiency who received treatment with sebelipase alfa in study LAL-CL01.

4.2 Number of Subjects

Up to 9 subjects will be enrolled in this study after successfully completing treatment in study LAL-CL01.

4.3 Inclusion Criteria

A subject must meet all of the following inclusion criteria to be eligible for this study:

- 1. Subject understands the full nature and purpose of the study, including possible risks and side effects, and is willing and able to comply with all study procedures and provide informed consent.
- 2. Subject received all 4 scheduled doses of sebelipase alfa in study LAL-CL01 with no life-threatening or unmanageable study drug toxicity.

- 3. Female subjects have a negative serum pregnancy test at screening, and are not breast-feeding.
- 4. Female subjects of childbearing potential are willing and able to use a highly effective and approved contraceptive method(s) from the date of informed consent until 30 days after last dose of IMP. A highly effective method of contraception is defined as fulfilling at least one of the following:
 - a. Strict abstinence;
 - b. Bilateral tubal ligation;
 - c. Combined oral contraceptives (estrogens and progesterone), inserted, applied, implanted or injectable contraceptives on a stable dose for at least 1 month prior to the screening visit;
 - d. Hormonal intra-uterine device (IUD) inserted at least 1 month prior to the screening visit;
 - e. Vasectomized partner for at least 3 months prior to the screening visit;
 - f. Condom with spermicide.

Women may be considered of non-childbearing potential if they are surgically sterile (i.e., total hysterectomy or bilateral salpingo-oophorectomy) or post-menopausal (defined as a complete cessation of menstruation for at least one year after the age of 45 years).

4.4 Exclusion Criteria

A subject who meets any of the following exclusion criteria will be ineligible for this study:

- 1. Clinically significant concurrent disease, serious inter-current illness, concomitant medications, or other extenuating circumstances that, in the opinion of the Investigator, would either interfere with study participation or the interpretation of the effects of sebelipase alfa.
- 2. Clinically significant abnormal values on laboratory screening tests, other than liver function or lipid panel tests. Subjects with an abnormal laboratory value that is of borderline significance may be allowed to undergo repeat testing once within a 30-day period.

4.5 Concomitant Medications and Treatments

Reasonable efforts will be made to ascertain all concomitant medications and treatments (pharmacological and non-pharmacological) received by the subject from the last assessment in study LAL-CL01 until completion of the follow-up visit approximately 30 days after the last dose of IMP. Concomitant medications include prescription and over-the-counter medications, herbal medications, prophylactic and therapeutic vaccines, vitamins, and dietary supplements. Concomitant treatments include diagnostic, palliative, or interventional procedures (e.g., surgery, physical therapy).

All concomitant medications and treatments will be recorded in the electronic case report form (eCRF). The following information will be recorded: name of the medication (brand or generic) or therapy, reason for use, start date, stop date, dose and route of administration (if applicable), and frequency of administration.

Dose adjustments or discontinuation of lipid-lowering medications may be considered in consultation with the Sponsor for medical reasons including reconsideration of the need for lipid lowering therapy based on longer-term effects of sebelipase alfa on lipid levels.

Information about any major changes in diet (e.g., initiation or termination of a low-cholesterol diet) should be documented in the electronic case report form (eCRF).

4.6 Discontinuation of Subjects from Treatment or Assessment

4.6.1 Premature Withdrawal from Study Participation

In accordance with the Declaration of Helsinki, subjects have the right to withdraw from the study at any time for any reason, without prejudice to further treatment.

The Investigator and Sponsor also have the right to withdraw subjects from the study at any time. Specific reasons for discontinuation may include but are not restricted to the following:

- Intercurrent illness
- AEs
- Pregnancy
- Protocol deviation or non-compliance
- Termination of the study by the Sponsor

Unnecessary withdrawals should be avoided as an excessive rate of withdrawal can render the study uninterpretable.

4.6.2 **Procedures for Discontinuation**

All subjects who discontinue from the study should be asked about the reason(s) for their discontinuation and about the presence of AEs. The date and the reason for discontinuation will be recorded in the eCRF.

A subject will be considered early terminated if he/she discontinues treatment in the study prior to the Sponsor notifying the Investigators that the study will end. A subject will be considered discontinued due to an AE if the subject received any infusion or partial infusion of the IMP, but did not complete the study because of an AE, whether or not considered drug related.

Subjects who prematurely discontinue treatment in the study will also be asked to complete all discontinuation assessments prior to withdrawal, if possible. Post-study SAEs will be reported according to Section 7.4 for all subjects prematurely discontinuing treatment in the study.

When a subject fails to return for scheduled assessments, the following efforts should be made to contact him/her to determine a reason for the failure to return: three phone attempts, including the date and time, to be documented in the subject's chart. If there is no response to the phone calls, a certified letter should be sent. After these efforts have been exhausted, a subject should be identified as lost to follow-up in the eCRF.

In the event that a subject dies, permission for an autopsy may be sought (through a separate informed consent form) from the subject's next of kin. Samples collected from these procedures will be used to further understand LAL Deficiency and the effect of ERT.

4.7 Subject Replacement Policy

Subjects who discontinue the study for any reason will not be replaced.

4.8 Subject Recruitment and Screening

Each Investigator (or designee) responsible for the clinical management of a subject in study LAL-CL01 will notify that subject of the potential to continue to receive treatment with sebelipase alfa in the current extension study.

Information about this study will be posted on the http://clinicaltrials.gov/ and https://www.clinicaltrialsregister.eu/ websites.

5 Schedule of Assessments and Study Procedures

The following Schedules of Assessments are presented in Appendix A:

- Screening through Week 24;
- Week 26 through Week 52;
- 52-week schedule of repeating assessments.

The Investigator may also perform an unscheduled visit at any time during the study at his/her discretion. Assessments performed at an unscheduled visit should be symptom directed, and will be recorded in the eCRF if the Investigator determines the subject may remain on IMP.

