5.1.9 Electrocardiogram

12-lead ECGs will be obtained at the timepoints specified in Appendix A. In addition, unscheduled ECG(s) should be obtained in any subject exhibiting cardiovascular symptoms (e.g., palpitations, chest pain or tightness, tachypnea) or clinically significant changes in resting heart rate. ECGs will be reviewed by the Investigator, or designee, and any abnormalities will be specified as clinically significant (CS) or not clinically significant (NCS). If deemed to be clinically significant, these abnormalities must be recorded as Adverse Events in the electronic case report form (eCRF). In the event of any unexpected findings, subjects should be appropriately evaluated in accordance with local procedures.

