7.1 Adverse Events and Laboratory Abnormalities

7.1.1 Clinical Adverse Events

An *Adverse Event* is any untoward medical occurrence in a subject, which does not necessarily have to have a causal relationship with the administration of an IMP. An AE can therefore be any unfavorable and unintended sign, symptom or disease temporally associated with the use of the IMP, whether or not considered related to the medicinal product. Pre-existing conditions that worsen in severity during the course of the study are to be reported as AEs.

All AEs occurring during the clinical study will be reported on the AE page of the eCRF.

The Investigator will assess the severity, causality (relationship to IMP), and seriousness of each AE.

Severity: The severity of AEs will be graded according to the National Cancer Institute Common Terminology Criteria for Adverse Events (CTCAE), version 4.0 or higher. The CTCAE displays Grades 1 through 5 with unique clinical descriptions of severity for each AE based on the general guideline below. Detailed instructions on grading of events by MedDRA system organ class and lower level term are available online.

- **Grade 1:** Mild; asymptomatic or mild symptoms; clinical or diagnostic observations only; intervention not indicated.
- **Grade 2:** Moderate; minimal, local or noninvasive intervention indicated; limiting age-appropriate instrumental activities of daily life (e.g., preparing meals, shopping for groceries or clothes, using the telephone, managing money).
- **Grade 3:** Severe or medically significant but not immediately life-threatening; hospitalization or prolongation of hospitalization indicated; disabling; limiting self-care activities of daily life (e.g., bathing, dressing and undressing, feeding self, using the toilet, taking medications, and not bedridden).
- **Grade 4:** Life-threatening consequences; urgent intervention indicated.
- **Grade 5:** Death related to AE.

Note: Severity is distinct from seriousness. Thus, a Grade 4 AE is not by default an SAE. An AE will be reported as serious only if the Investigator judges the event to meet the definition of an SAE as provided below.

Page 38 of 76

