7.2.2 Adverse Event Reporting Period

The study period during which AEs must be reported is defined as the period from the signature of written consent to the end of the study treatment follow-up. For this study, AEs will be reported from the date of written informed consent until completion of the follow-up visit at approximately 30 days after the last dose of IMP. If a subject experiences an SAE that is considered to be related to study treatment at any time after the study, it must be reported to the Sponsor.

Page 41 of 76

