7.3 Recording of Adverse Events

At each scheduled contact with the subject, the Investigator must seek information on AEs by specific questioning and, as appropriate, by examination. Information on all AE should be recorded in the source document, and also in the appropriate AE module of the eCRF. All clearly related signs, symptoms, and abnormal diagnostic procedure results should be recorded in the source document, grouped under one diagnosis.

Page 42 of 76

The date/time when the AE started and stopped, severity, seriousness, action taken with regard to the study drug, causality assessment, and outcome of the event will be recorded in the eCRF for each AE.

Any AEs/SAEs remaining unresolved after completion of the last scheduled visit (i.e., follow-up visit) should be recorded as ongoing in the eCRF. Ongoing AEs/SAEs should continue to be followed up for the period specified in Section 7.2.3, but without further recording in the eCRF. However, follow-up information on SAEs must be reported to the Sponsor as described in Section 7.4.

7.4 Reporting of Serious Adverse Events, Infusion Associated Reactions and Unanticipated Problems

Investigators and the Sponsor must conform to the AE reporting timelines, formats and requirements of the various entities to which they are responsible. At a minimum the events that must be reported are those that are:

- related to study participation,
- unexpected, and
- serious or involve risks to subjects or others (see definitions, Section 7.1).

If the SAE/IAR report is supplied as a narrative, the minimum necessary information to be provided at the time of the initial report includes:

- Protocol number
 •
- Investigator name and site number
- Subject number
- A description of the event
- Date of onset
- Time and amount of last IMP administration

- Current status
- Whether study treatment was discontinued
- The reason why the event is classified as serious (if an SAE)
- Investigator assessment of the relationship between the event and study treatment
- Severity

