8.7.3 Other Safety Data

Observed measurements and changes from baseline to study timepoints in vital signs (blood pressure, heart rate, respiratory rate, and temperature), and 12-lead ECG parameters will be summarized. Listings of abnormal findings/values for physical examinations, vital signs, and ECGs will be presented, as appropriate.

Concomitant medication/treatment data will be coded using the WHO-DRUG dictionary. All data will be listed, and the number and percentages of subjects receiving each concomitant medication/treatment will be tabulated.

Page **48** of **76**

8.8 Efficacy, Pharmacodynamic, and Patient Health-Related Quality of Life (HRQOL) Outcomes Analyses

Data will be presented for subjects in the Full Analysis Set. All data will be presented by study visit in subject data listings. Observed measurements and changes or percent changes from baseline to study timepoints in liver and spleen volumes and liver and spleen fat content, liver cholesteryl ester signature, serum transaminases, plasma lipids, and acute phase reactants (e.g., serum ferritin) will be summarized overall and by dosing regimen. The percentage of subjects with abnormal transaminases at each timepoint will also be summarized overall and by dosing regimen. Scores and changes from baseline to study timepoints for the SF-36[®], FACIT-Fatigue, and CLDQ will be summarized.

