8.11 Missing or Invalid Data

All data will be analyzed as they were collected in the database. Missing data will not be imputed using statistical methods.

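### Protocol Section 5 ties eCRF entry of unscheduled-visit assessments to the subject staying on IMP, so supporting measurements from a visit that ends treatment could go unrecorded

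*Protocol*

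**What the plan says.** The opening text of Protocol Section 5 lets the Investigator hold an unscheduled visit at any time. On content it says: "Assessments performed at an unscheduled visit should be symptom directed". On recording it says that these assessments "will be recorded in the eCRF if the Investigator determines the subject may remain on IMP". Nothing follows for the case where the Investigator decides the opposite.

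Section 5.1.9 gives one reason why such data would arise: "unscheduled ECG(s) should be obtained in any subject exhibiting cardiovascular symptoms".

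The rules for events carry no such condition. Section 7.1.1: "All AEs occurring during the clinical study will be reported on the AE page of the eCRF". Section 7.2.2: "AEs will be reported from the date of written informed consent until completion of the follow-up visit at approximately 30 days after the last dose". Section 7.3 adds that, besides start and stop times, "severity, seriousness, action taken with regard to the study drug, causality assessment, and outcome of the event will be recorded in the eCRF for each" reported event. Section 4.6.2 puts the date and reason for discontinuation in the eCRF.

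On analysis, Protocol Section 8.7.3 states: "Listings of abnormal findings/values for physical examinations, vital signs, and ECGs will be presented, as appropriate". Section 8.7.2 adds frequencies of abnormal laboratory values. Section 8.11 states: "All data will be analyzed as they were collected in the database. Missing data will not be imputed using statistical methods". SAP Section 5.3 says nearly the same.

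**The concern.** The rule makes recording depend on a treatment decision that may itself result from the findings. If a subject has symptoms and continues, the ECG and blood pressures from the visit are entered. If similar findings lead to stopping, a site reading the sentence literally need not enter them. Missingness that depends on the outcome is harder to defend than ordinary gaps, and here the protocol would create it.

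The data exposed are not incidental. The protocol synopsis and SAP Section 2.2.1 list changes in vital signs, physical examination, ECG and clinical laboratory tests among the primary safety endpoints, beside AEs, SAEs and IARs. Because data are analysed as collected and not imputed, a value that is never entered cannot appear in a listing or a count.

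**Working it through.** The documents give no figure on this point, so the check is mainly a comparison of recording rules, followed by one scale calculation.

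**Step 1. What reaches the database from an unscheduled visit that ends in stopping IMP**

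| Item | Route | Depends on the Section 5 condition? |
|---|---|---|
| AE with severity, seriousness, causality, action taken, outcome | AE page of the eCRF (7.1.1, 7.2.2, 7.3) | No |
| SAE or IAR | Report to the sponsor within 24 hours (7.2.1, 7.4.1), plus AE page | No |
| Date and reason for discontinuation | eCRF (4.6.2) | No |
| ECG or laboratory abnormality judged clinically significant | Recorded as an AE (5.1.9, 7.1.2) | No, as an event |
| Central-laboratory results | Direct from the laboratory (7.1.2) | No |
| Vital signs, ECG parameters, examination findings | Site entry in the eCRF | Yes |
| PT/INR, aPTT, urinalysis | Local tests (5.1.10), site entry | Yes |

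The last two rows are the gap. The AE fields in Section 7.3 do not ask for the underlying blood pressures, ECG intervals or examination detail.

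**Step 2. Whether another provision closes the gap**

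- Section 4.6.2 asks subjects who stop early to complete discontinuation assessments, but only if possible.
- The End of Study visit (Appendix A) falls 30 (+7) days after the last dose and omits serial vital signs. It cannot stand in for values at the time of the decision.
- Section 9.3 says clinical data not on the eCRF are captured and transferred to the sponsor, and Section 8.1 promises listings of all data collected. Neither names a dataset or route for these values. Section 9.3 also allows exceptions specified elsewhere in the protocol, and Section 5 can be read as one.
- The SAP has no rule for unscheduled-visit values.

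**Step 3. Ambiguity about paused dosing**

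Sections 7.1.3 and 7.6 and Appendix E allow dosing to be suspended and later resumed after Safety Committee review. Section 5 does not say whether a suspended subject counts as one who may remain on IMP, so two sites could treat the same situation differently.

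**Step 4. Where a lost value would show**

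Protocol Sections 8.7.2 and 8.7.3 summarise changes to study timepoints, and SAP Section 11.4 summarises vital signs as change from pre-dose. An off-schedule value would rarely enter those tables. It would matter mainly in the by-subject listings and abnormal-value frequencies.

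**Step 5. Scale**

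Section 4.2 allows up to 9 subjects and Section 4.7 allows no replacement. One subject is 1/9 = 0.111, or 11.1%. With the exact binomial intervals that Section 8.1 names for categorical endpoints:

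- 0 of 9: upper 95% limit = 1 − 0.025^(1/9) = 0.336, so 0% to 33.6%.
- 1 of 9: exact (Clopper-Pearson) limits 0.0028 and 0.4825, so about 0.3% to 48.2%.

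One omitted abnormal value can therefore turn a category from one subject to none. This describes the weight of one subject. It does not estimate how often the omission happens.

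**The case against.** The strongest reply is that the safety signal survives. A reader might infer from Section 5 that the findings which led to stopping are left out of the primary safety data. The documents do not support that. AEs, SAEs and IARs come first among the primary safety endpoints and their recording is unconditional, as are the action taken and the reason for discontinuation. A subject stopped for chest symptoms would still appear in the AE and discontinuation outputs. This part stands, and it limits the point to supporting measurements.

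Second, the text says *if*, not *only if*. That is correct, but if every assessment were to be entered regardless, the clause would have no function. The restrictive reading is the natural one.

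Third, the exposure is narrow. The specific stopping rules in Appendix E concern IARs and IgE or skin-test positivity. IARs arise mainly during an infusion or within 4 hours after it, at scheduled visits with their own vital-sign schedule (Section 5.1.8). The Section 5 sentence does not govern those visits. This also stands, and it makes affected visits likely to be few.

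Fourth, a reader might infer that the Safety Committee works from the same incomplete data. Nothing in Section 7.5.1 limits it to eCRF data, and Section 7.1.3 has it review a severe IAR together with other relevant safety data.

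**Conclusion.** The point holds in a limited form. Section 5 conflicts with the unconditional recording rules in Sections 4.6.2, 7.1.1, 7.2.2 and 7.3. It allows a site to omit site-recorded vital signs, ECG parameters, examination findings and local test results from an unscheduled visit that ends in stopping IMP. Event records, the reason for discontinuation and central-laboratory results are not at risk.

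Where the stop is for safety, the omission would tend to under-report abnormal values in listings and abnormal-value frequencies. It would be too strong to say that the bias always favours the drug: subjects also stop for other reasons, and the event would still be tabulated. The documents do not show that any such visit occurred or how often one would. Each affected subject would be 11.1% of a full sample of 9.

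The conclusion assumes that sites read the condition as restrictive and that no other undocumented route carries the values into the database. It deserves correction as an avoidable, outcome-dependent recording rule, but it does not threaten the study's main safety conclusions.

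**What to change.** In Protocol Section 5, replace the condition with: *All assessments performed at an unscheduled visit will be recorded in the eCRF, whether or not the subject remains on IMP.* This also removes the ambiguity about suspended dosing. Ask sites to enter data from source documents for any unscheduled visit that ended in interruption or discontinuation. State in the SAP that unscheduled values are included in the abnormal-value listings and frequencies already planned; no new table type is needed.

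The change concerns recording only and leaves clinical management as it is. It costs one sentence in an amendment, one in the SAP, and a small amount of extra data entry. The number of visits to back-enter cannot be stated from the documents.
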